5.3.2. Efficacy Period

The efficacy period in study 8HA01EXT will be used for the evaluation of bleeding and consumption endpoints. For a subject to have an evaluable efficacy period over the duration of study 8HA01EXT, he must have >0 day of treatment for an episodic regimen, and at least 2 prophylactic injections for prophylactic regimens.

The start and end, and the total duration of the efficacy period for a given treatment regimen in 8HA01EXT is the same as the start and end, and the total duration of that treatment regimen defined in Section 5.3.1 with the following exception to the definition of start, and the adjustments necessary due to surgical/rehabilitation periods.

Exception to the Definition of Start

For subjects who entered study 8HA01EXT during a surgical/rehabilitation period, if they are to be on a prophylactic regimen in study 8HA01EXT, then the efficacy period for the prophylactic regimen will start at the time of the first prophylactic dose following the end of the surgical/rehabilitation period (see Section 5.3.3). If they are to be on the episodic regimen in study 8HA01EXT, then the efficacy period for the episodic treatment regimen will start at 00:01 on the day following the end of the surgical/rehabilitation period (see Section 5.3.3).

Adjustments Due to Surgical/Rehabilitation Periods

For analysis purposes, the efficacy period for a given treatment regimen will be adjusted for all surgical/rehabilitation periods (major and minor). The start and end of the efficacy period for a given treatment regimen are adjusted as follows:

- For subjects on a prophylactic regimen before the start of a surgical/rehabilitation period, the efficacy period for the prophylactic regimen continues up to the last dose (for prophylaxis or a bleed) before the start of the surgical/rehabilitation period.
- For subjects on the episodic regimen before the start of a surgical/rehabilitation period, the efficacy period for the episodic regimen continues up to 1 minute before the start of a surgical/rehabilitation period.
- For subjects on a prophylactic regimen following the end of a surgical/rehabilitation period, the efficacy period for the prophylactic regimen starts or re-starts (depending on whether there is a treatment regimen change during the surgical/rehabilitation period) at the first prophylactic dose following the end of the surgical/rehabilitation period.
- For subjects on the episodic regimen following the end of a surgical/rehabilitation period, the efficacy period for the episodic regimen starts or re-starts (depending on whether there is a treatment regimen change during the surgical/rehabilitation period) at 00:01 on the day following the end of the surgical/ rehabilitation period.

Start and end dates/times for the efficacy period for given treatment regimens and treatment regimen changes will be adjusted for each surgery (major or minor) as necessary.

For subjects on a prophylactic regimen before the start of a surgical/rehabilitation period, the interval of time between the last dose before a surgical/rehabilitation period and the start of the surgical/rehabilitation period will not be attributed to the efficacy period for the prophylactic regimen. By definition, there should not be any treated bleeding episodes in this interval of time.

For subjects on a prophylactic regimen following the end of a surgical/rehabilitation period, bleeding episodes that occur after discharge from a rehabilitation facility but before the next prophylactic dose will be attributed to the surgical/rehabilitation period and hence not counted towards the annualized bleeding rate.

Adjustments Due to Large Injection Intervals

For analysis purposes, the efficacy period will also be adjusted to account for large intervals between injections resulting from missing data. Time between any 2 adjacent rFVIIIFc injections of greater than 28 days within a prophylactic treatment regimen will be removed from the efficacy period. The efficacy period prior to each such interval will end at the time of the first

injection of this interval and restart (or start if it is the first interval of a treatment regimen) at the time of the second injection of this interval. The efficacy period will be adjusted for each identified interval that is not within a surgical/rehabilitation period. Treatment regimens considered for large interval adjustment include tailored prophylaxis, weekly prophylaxis and personalized prophylaxis regimen with at least 2 routine prophylactic injections (additional injections are not considered due to the sporadic nature of these injections). No adjustment for large injection intervals will be made for episodic treatment regimens.

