5.3. Study Periods

5.3.1. Treatment Regimens for Analysis

For the purpose of analysis, the treatment regimen in study 8HA01EXT means the actual treatment regimen(s) that subjects follow over the course of the study (i.e., not necessarily the regimen they started on). For example, a subject who starts the study on the tailored prophylaxis regimen and switches to the weekly prophylaxis regimen will appear in both the tailored prophylaxis and weekly prophylaxis regimens in the summaries based on the time he spent in the respective regimens.

Start and End of Treatment Regimens

At the start of study 8HA01EXT, the start date and time of the starting treatment regimen is 8HA01EXT Study Day 1 with starting time defined below:

For 8HA01EXT subjects with no gap or a gap of less than or equal to 7 or 4 days:

In general, starting time is defined as either 1) 1 minute after the last rFVIII Fc dose on 8HA01EXT Study Day 1 for subjects on a prophylactic regimen in study 997HA301, 8HA02PED, 997HA307, or 997HA309, or 2) 23:59 on 8HA01EXT Study Day 1 for subjects on the episodic regimen in study 997HA301/997HA307 or subjects who ended the study in a surgical/rehabilitation period in study 997HA301, 8HA02PED, 997HA307, or 997HA309.

For subjects from study 997HA307/997HA309 who only had PK injections (i.e. no injections in treatment phase) and enroll in 8HA01EXT on a prophylactic regimen, the start time is either 1) the time of the prophylactic dose on Study Day 1, or 2) 23:59 on Study Day 1 if there is no prophylactic dose on Study Day 1. The time between 23:59 and 1 minute before the first prophylactic dose in study 8HA01EXT will be imputed as PK period.

For 8HA01EXT subjects with a gap of greater than 7 or 4 days:

Start time is defined as either 1) time of the first rFVIII Fc dose on 8HA01EXT Study Day 1 for subjects on a prophylactic regimen at the start of study 8HA01EXT, or 2) 00:01 on 8HA01EXT Study Day 1 for subjects starting study 8HA01EXT on the episodic regimen or in a surgical/rehabilitation period.

The above definition of the start date and time of the starting treatment regimen is applicable for all subjects with the following exceptions:

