During study 8HA01EXT, when a treatment regimen changes, the date of the prescribed change will be recorded on the 'Treatment Regimen Assignment Change Details (TRS2)' form in the eCRF. In the following sections, new treatment regimen refers to the one that the subject was changed to, and the previous treatment regimen refers to the one immediately before the new treatment regimen. The start date and time of the new treatment regimen and the end date and time of the previous treatment regimen are defined in the following three scenarios:

- From one prophylactic regimen to a new prophylactic regimen, the new prophylactic regimen starts at the date and time of the first prophylactic dose in the new prophylactic regimen. The previous prophylactic regimen ends 1 minute before that. If the time of the first prophylactic dose in the new prophylactic regimen is not available, the new prophylactic regimen will start at 00:01 on the day of the first prophylactic dose in the new prophylactic regimen, and the previous prophylactic regimen will end at 23:59 on the day prior to that.
- From the episodic regimen to a prophylactic regimen, the prophylactic regimen starts at the date and time of the first prophylactic dose in the prophylactic regimen. The episodic regimen ends 1 minute before that. If the time of the first prophylactic dose in the prophylactic regimen is not available, the prophylactic regimen will start at 00:01 on the day of the first prophylactic dose in the prophylactic regimen, and the episodic regimen will end at 23:59 on the day prior to that.
- From a prophylactic regimen to the episodic regimen, if there is no prophylactic dose on the day of treatment regimen change recorded in the eCRF, the episodic regimen starts at 00:01 on the day of treatment regimen change, and the prophylactic regimen ends at 23:59 on the day prior to the day of treatment regimen change. If there is a prophylactic dose on the day of treatment regimen change, the episodic regimen starts 1 minute after that prophylactic dose, and the prophylactic regimen ends on the date and time of that prophylactic dose.

Duration of a Treatment Regimen

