6.5.3. Prophylactic Dose (IU/kg) and Dosing Interval (days)

Because prophylactic dosing in study 8HA01EXT is based on variable doses and dosing intervals, the amount of rFVIII^{FC} received prophylactically will be summarized as an average weekly dose. Descriptive statistics will be provided using the FAS for each prophylactic regimen.

The average weekly prophylactic dose (IU/kg) and the prophylactic dosing interval will be based on prophylactic doses that are not separated by a bleeding episode. Data to be included in the calculations, specifically the prophylactic doses and the total duration of prophylaxis treatment, will come strictly from intervals representing 2 consecutive prophylactic doses (PR) during the efficacy period (see Section 5.3.2 for a description of the efficacy period). The sum of doses at PR_x and the sum of interval durations (PR_{x+1} minus PR_x) will be determined across all evaluable intervals of PR_x to PR_{x+1}. As such, when a bleeding episode is encountered, the interval stops at the prophylactic dose prior to the event and continues with the first prophylactic dose after the event. The last PR dose during a given treatment regimen will be the end of the last interval used for these calculations. The start and stop time of a treatment regimen and the calculation of total duration in that treatment regimen are described in Section 5.3.1. If a subject is treated in a given treatment regimen more than once during study 8HA01EXT, the sum of doses at PR_x, sum of days in PR intervals, sum of days in PR intervals and number of PR intervals will be calculated across all durations in that treatment regimen before the average weekly prophylactic dose and dosing interval are calculated using the formulae below.

$$\text{Average weekly prophylactic dose} = \frac{\text{Sum of doses at PR}_x}{\text{Sum of days in PR intervals}} \times 7$$

$$\text{Average prophylactic dosing interval} = \frac{\text{Sum of days in PR intervals}}{\text{Number of PR intervals}}$$

For the personalized prophylaxis regimen, additional injections administered will also be included in the average weekly prophylactic dose and average dosing interval calculations.

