6.5.4. Consumption

The total annualized rFVIII Fc consumption (IU/kg) will be calculated for each subject using the following formula:

$$\text{Annualized consumption} = \frac{\text{Total IU/kg of study drug received during the efficacy period}}{\text{Total number of days during the efficacy period}} \times 365.25$$

The total amount of rFVIII Fc received will be the sum of the nominal IU/kg administered for each injection based on the units of rFVIII Fc as recorded from the subject's diary and eCRF and his most recent weight.

Total annualized rFVIII Fc consumption will be determined for each treatment regimen during the efficacy period (i.e., excluding surgery/rehabilitation periods [major and minor surgeries]).

For personalized prophylaxis regimen, additional injections administered will be included in the consumption calculations.

Consumption is a secondary endpoint in this study. A description of how consumption will be summarized is provided in Section 7.3.3.

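### Annualized consumption (SAP 6.5.4) is one dose too high for each prophylaxis segment that both opens and closes at a counted dose, and one dose too low in one switch pattern

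*SAP*

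**What the plan says.** SAP 6.5.4 defines annualized consumption as "Total IU/kg of study drug received during the efficacy period" divided by "Total number of days during the efficacy period", times 365.25. It is calculated per subject and per treatment regimen. Neither 6.5.4 nor 7.3.3 says how to treat a dose given exactly at the start or end of the period.

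The boundaries come from SAP 5.3.1 and 5.3.2. For an evaluable efficacy period, 5.3.2 asks for "at least 2 prophylactic injections for prophylactic regimens".

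- **Openings that leave the opening dose out.** With no entry gap, or one of at most 7 days (4 days for subjects from the pediatric study), the period generally begins "1 minute after the last rFVIII Fc dose on 8HA01EXT Study Day 1 for subjects on a prophylactic regimen" in the parent study.
- **Openings at a dose.** After a longer entry gap the start is the "time of the first rFVIII Fc dose on 8HA01EXT Study Day 1 for subjects on a prophylactic regimen at the start of study 8HA01EXT". On a change from episodic treatment, "the prophylactic regimen starts at the date and time of the first prophylactic dose in the prophylactic regimen", and a change between prophylactic regimens works the same way. After surgery, major or minor, the period restarts at the first prophylactic dose. After a removed interval of more than 28 days it restarts "at the time of the second injection of this interval".
- **Closings at a dose.** These are the last dose of a final prophylactic regimen, the last dose before a surgical period, the first injection of a removed interval, and a change to episodic treatment on a day with a prophylactic dose.
- **Closings that leave the dose out.** On a change to another prophylactic regimen, the old one ends 1 minute before the new regimen's first dose.

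SAP 6.5.3 handles the same matter differently for the average weekly dose: "The sum of doses at PR_x and the sum of interval durations (PR_{x+1} minus PR_x) will be determined". There the last dose only ends the final interval and is not itself counted.

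**The concern.** A dose covers the time until the next one. If a segment begins at one dose and ends at another, and both are counted, the numerator holds one more dose than the denominator holds intervals.

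Consumption per kg per year is a named secondary endpoint (SAP 2.2.2). The error depends on how many surgeries, removed intervals, entry gaps and regimen changes a subject had, and not on how much drug he used. Subjects contribute to every regimen they followed, and each per-subject value has equal weight in that regimen's mean. A short stay on a regimen can therefore move the mean or set the maximum. The 2-injection minimum in 5.3.2 applies over the whole study, so a restarted segment holding a single dose can add one dose and zero days.

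**Working it through.** The documents give no consumption figure to reproduce, so the check applies the 6.5.4 formula to perfectly regular dosing under each boundary rule.

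**Inputs.** The dose is 65 IU/kg every 7 days, the weekly regimen in SAP 3.2.1.2, used here only to show size. Boundaries are from SAP 5.3.1 and 5.3.2. The 1-minute offsets change the number of days by a negligible amount.

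**True rate.** 65 / 7 × 365.25 = 3,391.6 IU/kg/year.

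**One segment of k = 52 intervals (364 days).**

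| Opens | Closes | Doses counted | Result (IU/kg/year) | Error |
|---|---|---|---|---|
| at a dose | at a dose | 53 | 65 × 53 / 364 × 365.25 = 3,456.8 | +1.9% |
| 1 min after parent dose | at a dose | 52 | 3,391.6 | none |
| at a dose | 1 min before new prophylactic regimen | 52 | 3,391.6 | none |
| 1 min after parent dose | 1 min before new prophylactic regimen | 51 | 65 × 51 / 364 × 365.25 = 3,326.4 | -1.9% |

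In the first row the excess is (k+1)/k - 1 = 1/k. In the last row the shortfall is also 1/k. A change to episodic treatment on a day without a prophylactic dose ends the segment at 23:59 the day before. That end is not tied to a dose, so it produces no fixed one-dose error.

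**Dependence on length (both ends at a dose, weekly).** 1 interval gives +100%, 13 give +7.7%, 26 give +3.8%, 104 give +1.0%, and 209 (about 4 years) give +0.5%. For an illustrative 50 IU/kg every 3 days, the excess is +0.8% at 1 year (122 intervals) and +0.2% at 4 years (487 intervals).

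**Breaks.** Suppose r of the 52 weekly intervals are removed for surgery or as long intervals. No dose is lost, and each restart opens at a dose. The ratio to the true rate is 52/(52 - r) after a no-gap start and 53/(52 - r) after a gap start.

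| r | No-gap start | Gap start |
|---|---|---|
| 0 | 0% | +1.9% |
| 1 | +2.0% | +3.9% |
| 2 | +4.0% | +6.0% |
| 4 | +8.3% | +10.4% |

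Over 209 weekly intervals with r = 4, the excess is 209/205 - 1 = 2.0% after a no-gap start, or 210/205 - 1 = 2.4% after a gap start.

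**Contrast between regimens.** Take a no-gap subject with 26 weeks of equal twice-weekly doses who then changes to weekly dosing for 26 weeks until his last dose. The first regimen is low by 1/52 (51 doses over 52 intervals, -1.9%). The second is high by 1/26 (27 doses over 26 intervals, +3.8%). The ratio is 1.0385 / 0.9808 = 1.059, a spurious difference of about 6%.

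**The case against.** A reader might infer that consumption is too high by one dose in every prophylaxis segment, so that the endpoint is inflated throughout. The documents do not support that. The entry rule that SAP 5.3.1 applies in general leaves the parent-study dose out, so an uninterrupted no-gap subject followed to his last dose has k doses over k intervals and no error. A segment opened at a dose and ended by a change to another prophylactic regimen is also exact.

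Nor does the 2-injection minimum imply a 100% excess. It is an evaluability condition and sets no boundary. Two injections after a no-gap start cover two intervals, and the doubling occurs only if the two injections are the two ends of a single segment.

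It is also fair to say that all analyses are descriptive, that follow-up may run to 4 years and dilutes the error, and that the documents do not say how often surgery, removed intervals or regimen changes occur.

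A further defence is that 6.5.4 never says outright that a dose at the boundary time is counted. However, where the SAP wants a dose outside a period it uses a 1-minute offset, which indicates that a dose at the stated time belongs to the segment. Leaving out both boundary doses would give k - 1 doses over k intervals, an error of the same size in the other direction. A boundary rule is needed on either reading.

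What stands is the mechanism, limited to the boundary combinations listed, and the inconsistency with 6.5.3.

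**Conclusion.** Followed as written, SAP 6.5.4 overstates annualized consumption by one dose for each prophylaxis segment that opens and closes at a counted dose. It understates it by one dose for a no-gap first segment that ends in a change to another prophylactic regimen. Other segments with dose-based ends are correct.

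The size is modest for long, unbroken segments: about 0.5% to 1.9% for weekly dosing over 4 years down to 1 year, and less for more frequent dosing. It matters for short or often-interrupted segments and for comparisons between regimens, where the errors can have opposite signs. These figures assume regular dosing, one interval lost per break, and that doses at boundary times are counted. The number of affected subjects is unknown. That consumption will in fact be distorted differently across regimens is a possibility shown by example, not something the documents establish.

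**What to change.** Add a boundary-dose rule to SAP 6.5.4:

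- Count each prophylactic dose against the time that follows it within its segment.
- Leave the closing prophylactic dose out of the numerator only when the segment also opened on a counted dose.
- Leave no-gap segments that end at a dose unchanged. Dropping a dose there would turn a correct 3,391.6 into about 3,326.4 in the 52-week example.
- For a no-gap first segment ended by a change to another prophylactic regimen, start the consumption denominator at the first counted dose (51 doses over 51 intervals in the example, which returns 3,391.6). Apply this to consumption only, not to the period used for the bleeding rate.
- Keep every bleed-treatment dose in the numerator, including one that closes a segment before surgery. Consumption covers treatment as well as prevention (SAP 7.3.3), so the 6.5.3 method cannot be copied over whole.

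With both ends at a dose, the 52-week example then falls from 3,456.8 to 3,391.6. The cost is SAP wording and a small programming change, with no new data. Reported figures would move slightly, mostly downward.

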5.3.3. Surgical/Rehabilitation Period

The broadest span of time for the surgical/rehabilitation period in study 8HA01EXT is from the first dose of rFVIIIIFc in study 8HA01EXT given for the surgery (i.e., the pre-surgery dose) up to 1 minute before the first regular prophylactic dose after the last day of postoperative care/rehabilitation for subjects on prophylactic regimens and up to 23:59 on the last day of the surgical/rehabilitation period for subjects on the episodic regimen. If dose(s) labeled for a surgical reason which do not correspond to a surgery will be re-classified as 'OTHER' and will not be used in the determination of the surgical/rehabilitation period. Since not all subjects will have these events, specific considerations for the start and end of the surgical/rehabilitation period are as follows:

Start of the surgical/rehabilitation period:

- Date/time of the first pre-surgical dose. In general, if an injection for a pre-surgical dose is recorded in the eCRF, the reason for the injection should be labeled as "prophylaxis pre-operative". If an injection for pre-surgical dose is recorded in the EPD, the reason will be labeled as "surgical prophylaxis". If the date/time of surgery is complete, a pre-surgery dose is any dose labeled for a surgical reason on the day of, or the day before surgery, which is prior to the start date/time of the surgery. If the time of surgery is missing or 00:00 (as sometime occurs for minor surgeries), only injections labeled as "prophylaxis pre-operative" on the day of surgery should be taken as a pre-surgical dose along with any other doses labeled for a surgical reason on the day before surgery. If there is more than one pre-surgical dose, then the first one should be selected (a pre-surgical dose can be administered the day before the surgery).
- If there is no pre-surgical dose but there was a prophylaxis dose or dose given for "OTHER" reason prior to the surgery on the day of or the day before surgery, the last of these doses should be selected.
- If there is no pre-surgical dose or a prophylaxis dose prior to the surgery on the day of or the day before surgery then select the start date/time of the surgery. If the time was not recorded or recorded as 00:00 then select the date and impute 00:01 for the time.

End of the surgical/rehabilitation period:

If the treatment regimen after the surgical/rehabilitation period is a prophylactic regimen, then the end of the surgical/rehabilitation period is

- 1 minute before the first prophylactic dose on or after the last date among the dates for discharge from the hospital, post-operative visit 1, post-operative visit 2, the end of rehabilitation.
- If all of the dates mentioned above are missing, then select the first prophylactic dose after the date/time for the end of surgery. If the surgery time was not recorded or recorded as 00:00, then select the surgery date and impute 23:59 for the time. If the end date of the surgery is missing, then select the start date of the surgery and impute 23:59 for the time.
- If there are no prophylaxis doses following the latter of the 6 dates mentioned above, then select the latter of the dates and impute 23:59 for the time if otherwise there is no time associated with the given date (e.g., the subject completed the surgical/rehabilitation period but received no further prophylactic doses).
- If the overall end of study is declared while the subject is still in the surgical/rehabilitation period, then select the date of the end of study and impute 23:59 for the time.

If the treatment regimen after the surgical/rehabilitation period is the episodic regimen, then the end of the surgical/rehabilitation period is

- Imputed as 23:59 on the last date among the dates for discharge from the hospital, post-operative visit 1, post-operative visit 2, and the end of rehabilitation
- If all of the dates mentioned above are missing, then select the date of the end of surgery and impute 23:59 for the time. If the end date of the surgery is missing, then select the start date of the surgery and impute 23:59 for the time.

Two exceptions are noted:

- If 2 (or more) major surgeries are performed without an intervening discharge from the hospital, then the first surgical/rehabilitation period will end 1 minute before the start of the next surgery and the second surgical/rehabilitation period will end as described above.
- If minor surgery is performed during postoperative care or rehabilitation then the surgical/rehabilitation period for the minor surgery will start and end on the day of the minor surgery, at 00:01 and 23:59, respectively, if times are not otherwise provided or recorded as 00:00. The surgical/rehabilitation period for the major surgery will include the minor surgery (ie, the surgical/rehabilitation period for the major surgery does not stop and restart around the minor surgery) and will end as otherwise defined.

Within the total surgical/rehabilitation period, the time is divided into:

- Intraoperative period: from the date/time of the pre-surgery rFVIIIIFc dose to the date/time of the end of surgery
- Postoperative care period: from the date and time plus 1 minute following the end of surgery to the last dose of rFVIIIIFc given for the surgery, including doses given to prevent bleeding during the postoperative period

- Postoperative rehabilitation period: from the date following the last day of postoperative care to the end of the surgical period as described above

The surgical/rehabilitation period will be determined in the same manner for both major and minor surgeries.

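### SAP 5.3.3 can end a minor-surgery period before the operation and lets the periods of two major surgeries overlap

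*SAP*

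**What the plan says.** SAP 5.3.2 takes all surgical/rehabilitation periods, major and minor, out of the efficacy period. On prophylaxis, the efficacy period stops at the last dose before the surgical period starts. It resumes at the first prophylactic dose following its end.

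SAP 5.3.3 sets the start:
- With complete surgery times, "a pre-surgery dose is any dose labeled for a surgical reason on the day of, or the day before surgery", given before the surgery starts; the first such dose is used.
- Failing that, a routine or OTHER dose given "prior to the surgery on the day of or the day before surgery, the last of these doses should be selected".
- Failing that, the start of the surgery.

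It sets the end, when prophylaxis follows, at "1 minute before the first prophylactic dose on or after the last date among the dates for discharge from the hospital", post-operative visits 1 and 2 and the end of rehabilitation. If all these dates are missing, the rule is instead to "select the first prophylactic dose after the date/time for the end of surgery". The opening description of the section lets the period run "up to 1 minute before the first regular prophylactic dose after the last day of postoperative care/rehabilitation". The section closes by applying the same derivation to minor surgery.

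For two or more major surgeries with no discharge in between, "then the first surgical/rehabilitation period will end 1 minute before the start of the next surgery".

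**The concern.** The end rule compares a dose with calendar dates and does not check that the dose came after the operation. The start rule, meanwhile, accepts a routine dose given before surgery on the same day. One dose can therefore satisfy both rules. The fallback for missing dates has the missing check, and the opening description says after, not on or after, the last day of care. The section thus disagrees with itself.

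In the exception for two major surgeries, the first period is cut at the next surgery, but the second period has already begun at its pre-surgery dose. The exception does not apply once the subject has been discharged.

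The first defect puts peri-operative time, bleeds and doses into the ABR and annualized consumption, from which SAP 5.3.2 and 6.5.4 exclude them. The second lets one dose belong to two surgeries in the summaries of SAP 7.6. These are separate consequences.

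**Working it through.** The plan states no figure here, so the check applies the rules literally to example records.

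**Part 1: end of the period.** Assumed: prophylaxis before and after; surgery from 10:00 to 10:30 on day D; routine doses every 3 days at 08:00 (D-3, D+3), plus the doses shown; discharge on D is the only date recorded.

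| Doses around surgery | Start | End | End minus start | Period covers surgery? |
|---|---|---|---|---|
| A. Labelled D 08:00 | D 08:00 | D+3 07:59 | +4,319 min | Yes |
| B. Routine D 08:00 only | D 08:00 | D 07:59 | -1 min | No |
| C. Labelled D 09:00, routine D 07:00 | D 09:00 | D 06:59 | -121 min | No |
| D. Labelled D-1 20:00, routine D 07:00 | D-1 20:00 | D 06:59 | +659 min | No |
| E. Routine D-1 20:00 only | D-1 20:00 | D+3 07:59 | +5,039 min | Yes |
| F. Labelled D 08:00, routine D 20:00 | D 08:00 | D 19:59 | +719 min | Yes |

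B, C and D share one feature: a routine dose earlier on the surgery date. All six patterns behave properly if every date is missing (the guarded fallback applies) or if a visit on D+10 exists. The protocol requires a visit 1-2 weeks after major surgery (7.1) and omits Visits 3 and 4 for minor surgery (surgery visit footnotes). The failure is therefore essentially confined to minor surgery.

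Effect on the efficacy period in pattern B:
- As written, it stops at D-3 08:00 and resumes at D 08:00, so 3 days are removed.
- With the fallback's guard, it would resume at D+3 08:00, so 6 days would be removed.
- The 3 days containing the surgery and early recovery are wrongly kept. Over the maximum 4 years, 3 / 1,461 = 0.2% of follow-up.

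Effect on the ABR (SAP 7.1.1: bleeds / days x 365.25) of one bleed wrongly counted, ignoring the small change in days:
- 1 year: 1 / 365.25 x 365.25 = 1.0
- 2 years: 1 / 730.5 x 365.25 = 0.5
- 4 years: 1 / 1,461 x 365.25 = 0.25

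**Part 2: two major surgeries, no discharge between.** Overlap = (second surgery start - 1 minute) - first pre-surgery dose of the second surgery.
- Dose 06:00, surgery 08:00 the same day: 07:59 - 06:00 = 1 h 59 min.
- Dose 08:00 the day before, surgery 08:00: 23 h 59 min.
- Extreme: dose 00:01 the day before, surgery 23:59: 47 h 57 min.

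Every dose in that window lies in both periods. SAP 7.6 obtains total dose by summing over the referenced time period. There is no overlap only when no qualifying dose precedes the second surgery.

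**Part 3: discharge between, regular prophylaxis not resumed.** The exception does not apply. The first period still waits for a prophylactic dose, so it can end at the same dose as the second and contain all of it.

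**The case against.** **Rarity.** Same-day discharge alone does not trigger the first defect; three of the six patterns are sound. It also needs subsequent prophylaxis, a dose labelled routine earlier that day and no later date. This stands, and it limits the point to minor surgery.

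**Other safeguards.** Protocol 10.1.3 has a pre-operative loading dose given on the day, which should be labelled surgical. SAP section 9 allows a routine dose to be relabelled as surgical prophylaxis without subject confirmation, which would remove pattern B. Protocol 10.1.3 also keeps bleeding directly caused by surgery from being reported. These reduce the frequency. However, relabelling happens record by record, the start rule itself expects unlabelled cases, and unexpected bleeding is still recorded.

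**Recoverable intent.** SAP 5.3.3 places the intraoperative period within the total period, so a period that ends before surgery is plainly unintended, and a negative length would show up in checks. That is fair for B and C. In pattern D the length is positive and looks normal.

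**Stronger readings.** A reader might infer that the surgery removes no time from the efficacy period. In pattern B it removes the 3 days before the pre-operative dose. Only in pattern C does the removed interval shrink to zero. A reader might also infer that overlapping periods distort the ABR. They do not, because the time is excluded either way. Nor do the documents support a specific inflation of consumption per major surgery. They give neither the number of such pairs nor the doses involved, and SAP 7.6 does not name the period over which that item is summed.

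**Conclusion.** Both derivation errors are real as written. The first is a minor-surgery edge case that leaves the surgery and the days to the next routine dose in the ABR and consumption (3 days under the assumed schedule). It is negligible for follow-up time but can add up to 1.0 to the ABR of a subject followed for one year. The second assigns doses to two major surgeries, over roughly 2 to 24 hours in the worked examples and at most about 48 hours within one admission. It has no stated limit after a discharge, and it touches only per-surgery summaries, in a subgroup that SAP 7.6 calls small and mainly reviews through listings.

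The clock times and the 3-day schedule are assumptions, and the number of affected surgeries is unknown. All analyses are descriptive, and the inhibitor endpoint is untouched. The overall effect is probably small, but a programmer following the text would obtain wrong periods or have to improvise.

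**What to change.** Amend SAP 5.3.3 as follows.

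1. First end bullet: end the period 1 minute before *the first regular prophylactic dose that is after the end of surgery (23:59 if the time is missing) and on or after the last of the listed dates*. Patterns B, C and D then end at D+3 07:59, giving +4,319, +4,259 and +5,039 minutes. A, E and F do not change.
2. First exception: *if a second major surgery starts before the first period has ended, with or without discharge, the first period ends 1 minute before the second surgical/rehabilitation period starts*. The overlap becomes zero.
3. Add that, in this situation, *the second period starts at the first dose recorded as pre-operative for the second surgery, or otherwise at the start of that surgery*. Without this, any surgically labelled post-operative dose of the first surgery given the day before would be taken as the second surgery's pre-surgery dose. Duplication would then become misattribution.

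The cost is a few sentences and a program change. No new data are needed, and no dosing or clinical rule is involved.
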